## **3.6 Data collection and analysis**

Data will be collected by study co-investigators with assistance from IT personnel at the respective hospital from patients records that were identified as eligible for the study according to the inclusion criteria above. According to their data, participants will be split into two groups:

1- Traditional OVD group

In this group of patients, the ICL was implanted utilizing both cohesive and dispersive ophthalmic viscosurgical device.

## 2- Reduced OVD group

In this group of patients, the ICL was implanted with the use of cohesive OVD only.

There is one primary outcome of interest which is the unaided visual acuity after the surgery, and several secondary outcomes including postoperative intraocular pressure, corneal specular microscopy parameters (ECD, CV and hexagonality), and the observed adverse events that can happen during the operation or postoperatively.

Data will then be stored electronically in a sheet format to enable for later statistical analysis.

Data collection was started at the conduct of the study in March 2024, and it is expected to be completed 3-4 months later.

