## 2 Aim(s) / Objective (s)

Is omitting dispersive viscoelastic from the standard surgical technique and utilizing only cohesive OVDs (in what we call it reduced- OVD technique) safe and suitable?

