### 3.3 Study Population

All refractive surgery candidates attending the above hospital for the purpose of phakic introcular lens implantation were included in the study. However, the initial group allocation occurred before the commencement of the study on the basis of surgeon and patient preference, thereby, randomization was on convenient basis.

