## **3.5 Study Interventions / Procedures**

After enrolment, the record of each participant is examined meticulously for completeness of preoperative and postoperative data pertaining to study including:

Patient age and gender, date of the procedure and its operative notes including laterality and surgical steps.

preoperative and postoperative assessments such as uncorrected and best corrected visual acuity, refractive error quantification both objectively utilizing an autorefractometer autorefractor Nidek ARK 1 (Nidek Inc, Gamagori, Japan) and subjectively as manifest refraction, clinical slit-lamp examination notes, intraocular pressure with air puff tonometers, AC depth assessment by Pentacam Scheimpflug (Oculus Optikgeräte GmbH Inc., Wetzlar, Germany), specular microscopy study of corneal endothelial cells (endothelial cell density (ECD), coefficient of variation (CV) and hexagonality) using Topcon SP-1p Specular Microscope (Topcon Corporation, Tokyo, Japan),

Typically, there is a preoperative visit and multiple postoperative visits extending over the period of 1-2 years after the procedure.

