### 4.2 Statistical methods

After collection of data from patients records and its subjection to thorough analysis for incompleteness and exclusion criteria, these data will be stored electronically in sheet formats for later analysis. All statistical test and subsequent analyses will be performed using SPSS version 26 (IBM statistical software). Data will be classified into categorical and numerical. Categorical variables were described using frequencies and percentages and were analysed using Chi-squared test. Numerical variables, described as mean  $\pm$  standard deviation, will be subjected to tests of normality to determine the appropriate statistical tests for inter- and intra-group comparisons. Unpaired t test or Mann-Whitney test was used to compare the two groups (traditional and modified OVD) according to fulfilled statistical assumptions. These two groups were compared for statistically significant difference regarding all parameters that were collected as per section 3.5 of this protocol. These statistical comparisons were made both preoperatively to determine baseline characteristics of the study participants and postoperatively to determine any significant difference between the two groups. Within the same group whether traditional or reduced OVD, all of the aforementioned parameters were compared again pre- and postoperatively this time using either one sample paired t test or Wilcoxon signed-rank test according to fulfilled statistical assumptions. Significance was considered at P value less than 0.05.

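### Groups are formed by the OVD used, not the technique intended, so cohesive-only eyes that were given dispersive OVD during implantation would leave the Reduced group uncounted

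*Combined protocol and SAP*

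**What the plan says.** The aim (section 2) asks about a technique: "Is omitting dispersive viscoelastic from the standard surgical technique and utilizing only cohesive OVDs", and whether doing so is safe and suitable. On how patients came to one technique or the other, section 3.3 says that "the initial group allocation occurred before the commencement of the study on the basis of surgeon and patient preference".

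Section 3.6 then builds the analysis groups from the records: "According to their data, participants will be split into two groups". The Traditional group is defined by "In this group of patients, the ICL was implanted utilizing both cohesive and dispersive ophthalmic viscosurgical device", and the Reduced group by "In this group of patients, the ICL was implanted with the use of cohesive OVD only". Both definitions describe what was used, not what was planned.

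The material for this split comes from section 3.5, which lists "date of the procedure and its operative notes including laterality and surgical steps". The planned technique is not a listed item. Secondary outcomes include "the observed adverse events that can happen during the operation or postoperatively". Section 4.2 compares the two groups without adjustment. No section says what happens to an eye that began under one technique and finished under the other.

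**The concern.** Under section 3.6, group membership can be settled by something that happens after surgery has begun. If dispersive OVD is added because a cohesive-only implantation proves difficult, that event bears directly on whether omitting it was suitable. The same event disqualifies the eye from the Reduced group. Any complication in that eye would then count against the Traditional group, and complications during the operation are themselves an outcome.

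This differs from ordinary confounding by preference. The label would depend on an event during the procedure, so adjusting for baseline characteristics would not repair it. Adverse events are the outcome most exposed. A reader would also not learn how many cohesive-only attempts were completed as such, since the plan asks for no conversion count.

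**Working it through.** The plan states no sample size, event rate or conversion rate, so there is no figure of its own to reproduce. The check is a reading of the definitions, followed by arithmetic on assumed inputs.

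**Step 1: apply the definitions to a converted eye.** Take an eye begun with cohesive OVD alone.

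| What happened | Meets Reduced wording? | Meets Traditional wording? |
|---|---|---|
| No dispersive OVD used | Yes | No |
| Dispersive OVD added during implantation | No (not cohesive only) | Yes (both types used) |
| Dispersive OVD added after the lens was in place | Unclear | Unclear |

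Section 3.3 does not settle rows two and three, because it never says that the preference-based allocation is the one analysed.

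**Step 2: counts, worst case.** Assume 100 eyes planned per technique, with adverse events in 3 Traditional and 6 Reduced. Move *m* converted eyes, *x* of them with an event, from Reduced to Traditional:

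Traditional = (3 + x)/(100 + m); Reduced = (6 − x)/(100 − m).

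| m | x | Traditional | Reduced |
|---|---|---|---|
| 0 | 0 | 3/100 = 3.0% | 6/100 = 6.0% |
| 1 | 1 | 4/101 = 4.0% | 5/99 = 5.1% |
| 2 | 2 | 5/102 = 4.9% | 4/98 = 4.1% |
| 4 | 4 | 7/104 = 6.7% | 2/96 = 2.1% |
| 4 | 0 | 3/104 = 2.9% | 6/96 = 6.3% |

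In rows two to four every converted eye has an event, so these are worst cases. The last row has four event-free conversions, and the shift goes against the Reduced technique.

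**Step 3: the condition for the direction.** Moving the eyes raises the Traditional rate if x/m exceeds 3/100, and lowers the Reduced rate if x/m exceeds 6/100. Both shifts favour the Reduced technique only if converted eyes have a higher event rate than the eyes they leave and the eyes they join.

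**Step 4: expected rates.** Assume 100 eyes planned per technique. Let *b* be the event risk in Traditional and unconverted Reduced eyes, *r* the risk in converted eyes, and *c* the conversion rate.

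- By planned technique: Reduced = (1 − c)b + c·r; Traditional = b.
- By OVD used: Reduced = b; Traditional = (100b + 100c·r)/(100 + 100c).

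With b = 5%, r = 50%, c = 2%:

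- Planned: 0.98 × 5% + 0.02 × 50% = 5.9% versus 5.0%. Reduced minus Traditional is +0.9 points.
- Used: 5.0% versus (5 + 1)/102 = 5.9%. The difference is −0.9 points.

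Over b = 3% or 5%, r = 30% or 50% and c from 2% to 10%, the difference runs from +0.5 to +4.7 points by planned technique, and from −0.5 to −4.3 by OVD used. At c = 0 both are zero.

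**The case against.** The strongest reply is that the documents mention no conversion, rescue use or crossover. A reader might infer that failures of the new technique have been moved into the comparator. The documents do not support that: they show only that the rule would move such eyes if there were any.

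A second reply is that the groups can be read as techniques. Patient preference precedes surgery, section 2 speaks of technique, and section 6 places traditional dispersive use in the loading and implantation steps, which suggests planned use. This is a fair reading of intent. But section 3.6 holds the only operative definitions, and they turn on use, so the two sections still need to be reconciled.

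A third reply is that the bias need not favour the Reduced technique. This stands. A reader might infer a one-way bias across adverse events, ECD and IOP. For adverse events the direction depends on the condition in Step 3 of the working, and event-free conversions push the other way. For ECD, IOP and the primary outcome, unaided visual acuity, the documents give nothing from which to derive a direction.

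It is also true that none of the illustrative tables reaches the plan's 0.05 threshold. Fisher's exact test gives p = 0.50 with no relabelling, and 0.75, 1.00 and 0.17 for one, two and four relabelled eyes with events. What changes is the estimated direction, not the declaration of significance.

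Finally, the records may not show intent. That limits the fix but does not remove the need to state the rule.

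**Conclusion.** The point holds in conditional form. As written, section 3.6 groups by OVD used, differs from the allocation described in section 3.3, and leaves conversions without a rule or a count. An eye converted during implantation cannot be Reduced and fits Traditional; one converted after the lens was in place has no clear group.

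Bias in favour of the Reduced technique on adverse events requires two things that the documents do not show: that conversions occurred, and that converted eyes had more events than the others. With no conversions the bias is zero. Otherwise its size is unknown, and the figures above rest wholly on assumed inputs. They show that when events are rare, a few eyes can change the direction of the difference. No effect on the primary outcome is shown.

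The change should be made. The study's question is suitability, and conversions are direct evidence on it whatever their effect on the rates.

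**What to change.** Amend section 3.6, and align it with section 3.3, as follows:

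1. Group eyes by the technique the surgeon set out to use, as read from the operative notes and the sequence of surgical steps. An eye begun with cohesive OVD alone stays in the Reduced group for analysis whatever was added later.
2. Report the number of conversions in the Reduced group, with reasons, including a count of zero.
3. Give the OVD-used grouping as a sensitivity analysis.
4. Where intent cannot be read, show the results with those eyes placed in each group in turn.
5. State that unclear intent does not count as missing data under section 3.7. Otherwise the complete-data rule could exclude the very eyes that item 4 is meant to examine.

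The cost is a change of wording and one extra field from notes already being extracted under section 3.5. The drawback is that the notes may not show intent for an unknown share of eyes. If that share is large, the two-way analysis will give a wide range, and this should be stated as a limitation.

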## 1 Background

Refractive errors (myopia, hyperopia and astigmatism) are quite prevalent worldwide, they constitute the most common cause of visual impairment with myopia in particular being progressively increasing in its prevalence so that it is predicted that by 2050 nearly half of the world population will be myopic. Management modalities include correction with glasses, contact lenses, laser vision correction, intracorneal implants and intraocular refractive procedures such as phakic intraocular lens (PIOL) implantation which involves the use of implantable collamer lens (ICL) in many cases. PIOLs are being extensively used since they preserve the integrity of the cornea and thereby attaining higher quality of vision compared with conventional kerato-refractive procedures. Furthermore; they allow broader range of refractive errors to be corrected. The Staar V4c EVO visian ICL (Staar surgical Inc, Lake Forest, CA, USA) has demonstrated effectiveness and an excellent safety profile with more than one million ICL implants had already been performed globally. However, complications such as raised intraocular pressure (IOP), cataract and pupillary block do happen. The ICL implantation procedure typically utilizes viscoelastics to facilitate introduction and positioning of the implant. Viscoelastics should be removed thoroughly at the conclusion of the procedure, and failure to do so may induce early postoperative IOP rise. It is logical to assume that viscoelastics use during surgery increases operation cost and time due to the extra steps involving the injection and removal of the substance. Increased manipulation during ICL implantation surgery and irrigation required to ensure adequate removal of viscoelastics may encourage cataract formation as well. Few studies investigated the safety and efficacy of ICL implantation without the use of viscoelastics, where they implemented balanced salt solution (BSS) instead as a novel technique. In the present study we retrospectively investigated the safety and efficacy of modifying ICL implantation technique by using cohesive OVD only without using dispersive OVDs.

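### The sole primary outcome, unaided visual acuity, serves the efficacy part of the aim but is insensitive to many of the safety outcomes, so a null primary result cannot support a claim of safety

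*Combined protocol and SAP*

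**What the plan says.** Section 2 states the only research question. It opens "Is omitting dispersive viscoelastic from the standard surgical technique and utilizing only cohesive OVDs" and goes on to ask whether this is safe and suitable. Section 1 (Background) words the purpose more broadly: "we retrospectively investigated the safety and efficacy of modifying ICL implantation technique by using cohesive OVD only without using dispersive OVDs".

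Section 3.6, under the Reduced OVD group heading, says "There is one primary outcome of interest which is the unaided visual acuity after the surgery". The same sentence lists "several secondary outcomes including postoperative intraocular pressure, corneal specular microscopy parameters (ECD, CV and hexagonality), and the observed adverse events". No visit, scale or margin is attached to any of these outcomes.

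Section 4.2 treats every outcome alike: "These two groups were compared for statistically significant difference regarding all parameters that were collected as per section 3.5 of this protocol", and "Significance was considered at P value less than 0.05". Section 4.1 describes a convenience sample and gives no sample size, power or effect size.

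The Background supplies the safety context. It says that "complications such as raised intraocular pressure (IOP), cataract and pupillary block do happen", and, on removing viscoelastic at the end of surgery, that "failure to do so may induce early postoperative IOP rise".

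**The concern.** A primary outcome should be able to move if the answer to the main question is unfavourable. Here the question leads with safety, while the one primary outcome is a measure of visual result. Unaided acuity depends heavily on residual refractive error, which section 3.5 records separately. An eye can lose endothelial cells, or have a pressure rise that resolves, and still read the same unaided line.

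The study could therefore report no significant difference on its primary outcome whether or not the reduced technique carries a safety cost, and nothing in the plan says how such a result may be interpreted. The outcomes that do bear on safety are secondary and compared by difference tests alone. A non-significant P value on them, in a sample of unspecified size, does not show safety either.

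**Working it through.** **1. Figures in the plan.** There is none to reproduce. The only numeric design input is the 0.05 significance level, taken here as two-sided because the plan does not say. All other numbers below are assumptions for illustration, including the logMAR scale, the SDs, 100 per group, independent eyes and comparable groups.

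**2. Each safety outcome set against unaided acuity.**

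| Safety outcome in the plan | Effect on mean unaided acuity |
|---|---|
| Moderate fall in ECD; change in CV or hexagonality | Essentially none |
| Transient IOP rise | Essentially none once resolved |
| Cataract | Lowers acuity in the affected eyes; shifts the group mean only slightly if few are affected |
| Other adverse events | Only if they reduce vision, and then diluted in the same way |

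For the first two rows the true acuity difference is about 0. With comparable groups the primary test then rejects in about 5% of studies, as it would if the technique were harmless.

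**3. Dilution of harm that does reduce vision.** Suppose an extra fraction p of eyes in the reduced-OVD group each lose D logMAR.

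- Shift in the mean = p × D.
- Standard error at 100 per group, SD 0.10: 0.10 × √(2/100) = 0.01414.
- Chance of a significant result in the harmful direction = Φ(shift/0.01414 − 1.96).
- Number per group for 80% power = 2 × 7.849 × 0.10² / shift², where 7.849 = (1.960 + 0.8416)².

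| p | D | Shift | Chance at 100 per group | Per group for 80% power |
|---|---|---|---|---|
| 1% | 0.2 | 0.002 | 3.4% | 39,245 |
| 2% | 0.2 | 0.004 | 4.7% | 9,812 |
| 1% | 0.5 | 0.005 | 5.4% | 6,280 |
| 2% | 0.5 | 0.010 | 10.5% | 1,570 |
| 5% | 0.2 | 0.010 | 10.5% | 1,570 |
| 5% | 0.5 | 0.025 | 42.4% | 252 |

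With no harm at all, the chance in that direction is 2.5%. The table also flatters acuity, because it holds the SD at 0.10 although the affected eyes widen the spread. In the last row the reduced-OVD variance becomes 0.01 + 0.05 × 0.95 × 0.5² = 0.0219. The standard error is then √((0.01 + 0.0219)/100) = 0.0179, and the chance falls to Φ(0.025/0.0179 − 1.96), about 29%.

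**4. A safety measure already collected.** For a difference of 100 cells/mm² in ECD at 100 per group, assuming an SD of 200 to 300:

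- SD 300: Φ(100/(300 × √0.02) − 1.96) = Φ(0.40) = 65%.
- SD 200: Φ(100/(200 × √0.02) − 1.96) = Φ(1.58) = 94%.

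**5. Why a difference test is not enough for safety.** If no adverse events are seen in n eyes, the one-sided 95% upper bound on the true rate is 1 − 0.05^(1/n). This gives 5.8% for n = 50, 3.0% for n = 100 and 1.5% for n = 200. Whether such a bound counts as safe depends on a threshold, and the plan sets none.

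**The case against.** The strongest case on the other side has five parts.

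- **Acuity is relevant to the aim.** Section 1 names efficacy and section 2 asks about suitability. This stands, and is why acuity should remain a primary outcome.
- **Acuity is not blind to harm.** A reader might infer that it cannot register harm at all. The documents do not support that: the Background names cataract, which can lower unaided acuity, and section 3.5 describes follow-up of typically one to two years. Insensitive is the defensible word.
- **Safety is studied.** A reader might infer that the plan ignores it. It does not: section 4.2 compares IOP and the endothelial parameters between groups at the same 0.05 level. Without a hierarchy or sample size, the primary label also does little formal work. The limit applies to what the primary result can support, not to the whole study.
- **The documents do not name the harms of omitting a dispersive OVD.** The Background ties IOP rise to retained viscoelastic, and possible cataract to manipulation and to the irrigation needed to remove it. On that reasoning less OVD might help. Nothing says that dispersive OVD protects the endothelium; the relevance of ECD is inferred from its being an outcome. This weakens any case for ECD as the only acceptable choice, but IOP and adverse events bear on safety without that inference.
- **No passage says that a null acuity result will be reported as safety.** That is correct. The plan simply does not prevent it.

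One further caution stands. Allocation followed surgeon and patient preference (section 3.3), so confounding could move any of these comparisons away from the rates shown above.

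**Conclusion.** The mismatch holds. The aim leads with safety, the single primary outcome measures visual result, and no section justifies acuity as a measure of safety. Under the assumed inputs, vision-reducing harm in an extra 1–5% of eyes would be detected in the harmful direction in about 3% to 42% of studies with 100 per group. Harm that spares vision would not be detected beyond the false-positive rate. These figures rest on an assumed SD, event rate, size of loss and sample size, none of which the plan gives.

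A null primary result therefore cannot support a conclusion of safety. That conclusion has to come from the secondary outcomes, which have no margin and no precision statement. It does not follow that the study is unable to address safety, nor that the primary outcome should simply be swapped: the data are there, and a wholesale switch after extraction began in March 2024 would invite the charge of outcome switching.

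**What to change.** In section 3.6, before any between-group analysis:

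- Add a safety measure already collected as a co-primary outcome at a fixed postoperative visit, for example each eye's percentage change in ECD from its preoperative value, or postoperative IOP. Keep unaided acuity as the efficacy primary. Choose a visit window that the records can support and that suits the measure, since the Background's concern with IOP is an early rise.
- Report the between-group differences in ECD, IOP and adverse events with 95% confidence intervals.
- Prespecify an important difference for each. State that any conclusion of safety rests on whether the interval excludes that difference, not on a non-significant P value and not on acuity.
- Date the change and declare what data had been accessed by then.

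If outcome data have already been compared, leave acuity as primary, limit its conclusion to visual outcome and label the safety results descriptive.

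The cost is a dated amendment after extraction has begun, the work of justifying the important differences, and a little more analysis. No new measurements are needed: ECD and IOP are listed in section 3.5. Adverse events are named in section 3.6 but are not a separate item in section 3.5, so they should be added to that list, to bring them within the comparison that section 4.2 describes. The precision available for ECD will depend on its variability and on the final number of records, neither of which the plan states.
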